8.3.2 Definition of Serious Adverse Event (SAE)

An AE or suspected adverse reaction is considered serious (i.e., is an SAE) if, in the view of either the investigator or the Sponsor, it results in any of the following outcomes:

- Death;

- A life-threatening AE;
- Inpatient hospitalization or prolongation of existing hospitalization;
- A persistent or significant incapacity or substantial disruption of the ability to conduct normal life functions; or
- A congenital anomaly/birth defect.

Important medical events that may not meet the above criteria may be considered serious when, based upon appropriate medical judgment, they may jeopardize the subject and may require medical or surgical intervention to prevent one of the outcomes listed in this definition. Examples of such medical events include allergic bronchospasm requiring intensive treatment in an emergency room or at home, blood dyscrasias, convulsions that do not result in inpatient hospitalization, or the development of drug dependency or drug abuse.

“Life-threatening” refers to an AE that at occurrence represents an immediate risk of death to a subject. An event that may cause death if it occurs in a more severe form is not considered life-threatening. Similarly, a hospital admission for an elective procedure is not considered a SAE.

All SAEs, as with any AE, will be assessed for severity and relationship to study intervention.

All SAEs will be recorded on the SAE CRF.

All SAEs will be followed through resolution or stabilization by a licensed study physician (for IND studies, a physician listed on the Form FDA 1572 as the site PI or Sub-Investigator).

All SAEs will be reviewed and evaluated by DMID and will be sent to the DSMB (for periodic review), and the IRB/IEC.

8.3.3 Suspected Unexpected Serious Adverse Reactions (SUSAR)

A SUSAR is any SAE where a causal relationship with the study product is at least reasonably possible but is not listed in the IB, Package Insert, and/or Summary of Product Characteristics.

8.3.4 Classification of an Adverse Event

The determination of seriousness, severity, and causality will be made by an on-site investigator who is qualified (licensed) to diagnose AE information, provide a medical evaluation of AEs, and classify AEs based upon medical judgment. This includes but is not limited to physicians, physician assistants, and nurse practitioners.

8.3.4.1 Severity of Adverse Events

All AEs and SAEs will be assessed for severity using the NIAID Division of AIDS (DAIDS) Table for Grading the Severity of Adult and Pediatric Adverse Events, Corrected Version 2.1 (July 2017).²

For AEs not included in the Table, the following guidelines will be used to describe severity. In addition, all deaths related to an AE are to be classified as grade 5 according to the DAIDS Table.²

- Moderate (Grade 2): Events that are usually alleviated with additional specific therapeutic intervention. The event interferes with usual activities of daily living and causes discomfort but poses no significant or permanent risk of harm to the research subject.
- Severe (Grade 3): Events that interrupt usual activities of daily living, or significantly affect clinical status, or may require intensive therapeutic intervention. Severe events are usually incapacitating.
- Severe (Grade 4): Events that are potentially life threatening.
- Deaths (Grade 5): All deaths related to an AE are to be classified as SAEs.

8.3.4.2 Relationship to Study Intervention

For each reported adverse reaction, the PI or designee must assess the relationship of the event to the study product using the following guideline:

- Related – There is a temporal relationship between the study intervention and event, and the AE is known to occur with the study intervention or there is a reasonable possibility that the study intervention caused the AE. Reasonable possibility means that there is evidence to suggest a causal relationship between the study intervention and the AE.
- Not Related – There is not a reasonable possibility that the administration of the study intervention caused the event, there is no temporal relationship between the study intervention and event onset, or an alternate etiology has been established.

8.3.5 Time Period and Frequency for Event Assessment and Follow-Up

For this study, all AEs that are captured as part of the study (as defined above) and SAEs occurring from the time the informed consent is signed through the Day 29 visit will be documented, recorded, and reported.

8.3.5.1 Investigators Reporting of AEs

Information on all AEs that are captured as part of the study (as defined above) and SAEs will be reported on the appropriate CRF. These AEs and SAEs will also be described in terms of duration (start and stop date), severity, association with the study product, action(s) taken, and outcome.

Grade 1 and Grade 2 laboratory abnormalities and vitals are not expected to be reviewed, assessed or reported as adverse events.

Abnormal vital signs and clinical parameters attributed to the underlying COVID syndrome by the site PI or appropriate sub-investigator, even if meeting the Grade 3 or Grade 4 criteria, should not be reported as adverse events. This includes, but is not limited to, changes in O2 saturation, heart rate, respiration rate, & blood pressure.

8.3.6 Serious Adverse Event Reporting

8.3.6.1 Investigators Reporting of SAEs

Any AE that meets a protocol-defined criterion as a related SAE must be submitted within 24 hours of site awareness on an SAE form to the DMID Pharmacovigilance Group, at the following address:

DMID Pharmacovigilance Group
Clinical Research Operations and Management Support (CROMS)
[name]
[name]
SAE Hot Line: [name] (US) or [name] (outside US)
SAE [contact] (US) or [name] (outside US)
SAE Email Address: [contact]

Other supporting documentation of the event may be requested by the DMID Pharmacovigilance Group and should be provided as soon as possible. The DMID Medical Monitor will review and assess the SAE for regulatory reporting and potential impact on study subject safety and protocol conduct.

At any time after completion of the study, if the site PI or appropriate sub-investigator becomes aware of an SAE that occurred during the subject's participation in the study, the site PI or appropriate sub-investigator will report the event to the DMID Pharmacovigilance Group.

8.3.6.2 Regulatory Reporting of SAEs

Following notification from the site PI or appropriate sub-investigator, DMID, as the IND Sponsor, will report any SUSAR in an IND safety report to the FDA and will notify all participating site PIs as soon as possible. DMID will report to the FDA any unexpected fatal or life-threatening suspected adverse reaction as soon as possible, but in no case later than 7 calendar days after the Sponsor's initial receipt of the information. If the event is not fatal or life-threatening, the IND safety report will be submitted within 15 calendar days after the Sponsor determines that the information qualifies for reporting as specified in 21 CFR Part 312.32. Relevant follow up information to an IND safety report will be submitted as soon as the information is available. Upon request from the FDA, DMID will submit to the FDA any additional data or information that the agency deems necessary, as soon as possible, but in no case later than 15 calendar days after receiving the request.

SAEs that are not SUSARs will be reported to the FDA at least annually in a summary format which includes all SAEs.

Sites may have additional local reporting requirements (to the IRB and/or national regulatory authority).

8.3.7 Reporting of Pregnancy

Pregnancy is not an AE. However, any pregnancy that occurs during study participation should be reported to the Sponsor on the appropriate CRF. Pregnancy should be followed to outcome and the outcome will be captured and reported if necessary.

8.4 Unanticipated Problems

8.4.1 Definition of Unanticipated Problems

An Unanticipated Problem (UP) is any event, incident, experience, or outcome that meets the following criteria:

- Unexpected in terms of nature, severity, or frequency given (a) the research procedures that are described in the protocol-related documents, such as the IRB-approved research protocol and informed consent document; and (b) the characteristics of the subject population being studied;
- Related to participation in the research (meaning there is a reasonable possibility that the incident, experience, or outcome may have been caused by the procedures involved in the research); and
- Suggests that the research places subjects or others at a greater risk of harm (including physical, psychological, economic, or social harm) than was previously known or recognized.

8.4.2 Unanticipated Problem Reporting

To satisfy the requirement for prompt reporting, all UPs will be reported using the following timeline:

- UPs that are SAEs will be reported to the IRB and to the Statistical and Data Coordinating Center (SDCC)/study Sponsor within 24 hours of the investigator becoming aware of the event per the above describe SAE reporting process.
- Any other UP will be reported to the IRB and to the SDCC/study Sponsor within 3 days of the investigator becoming aware of the problem.

9. STATISTICAL CONSIDERATIONS

This is an adaptive platform study is intended to allow for several adaptations: 1) stopping enrollment into arms based on interim analyses of futility and efficacy and 2) addition of new experimental arm(s) into one stage, or 3) addition of separate study stages.

BET is a proof of concept study with the intent of identifying promising treatments that warrant future studies. Estimates produced from BET will also provide an improved basis for designing the future trials, in terms of sample size and endpoint selection. While the primary endpoint is Day 8 ordinal score, there is strong interest in analyses of secondary endpoints in assessing promise. The trial will enroll 100 patients per intervention and this will be compared with 100 control patients. Futility and early efficacy will be assessed after approximately 50 patients have been enrolled in the treatment and control arms. The interim analysis will find an intervention futile if its point estimate for the primary endpoint has an odds ratio <1 . An intervention can be declared efficacious early after 50 patients per arm if two-sided $p < .001$. If the intervention continues to 100 patients, it will be declared promising if the final two-sided p -value is $< .20$ and

will be considered as statistically significant if the final two-sided p-value < .05. Details of the statistical plan will be described in the statistical analysis plan (SAP).

Addition of new experimental therapies: If additional experimental arms are added, the sample size per arm will remain at 100. Analyses of newly added arm(s) will be performed comparing concurrently enrolled control subjects. This principle is used in general, that is, patients on interventions will only be compared to control patients who could potentially have been randomized to that intervention (i.e., they met eligibility criteria for the intervention and are at a site where the intervention was enrolling at the time of the patient's randomization.)

Statistical Hypotheses

The primary null hypothesis being tested is that proportions of subjects at each level of the 8-point ordinal scale does not differ at Day 8 between the experimental and control arms. For this, the parameter of interest is the "common odds ratio," which quantifies the shift in the severity distribution resulting from treatment. For an efficacious treatment, an odds ratio greater than 1 quantifies an improvement in disease severity; a value of 2 indicates a bigger improvement than a value of 1.25. The null hypothesis to be tested is that the odds of improvement on the ordinal scale is the same for the placebo and experimental treatment arms (i.e., the common odds ratio is 1). It is worth noting that, for large sample sizes, the test based on the proportional odds model is nearly the same as the Wilcoxon rank sum test.

9.1 Sample Size Determination

We have chosen a sample size of 100 per arm for this proof of concept study. The power can be computed for the Day 8 ordinal score on the basis of an odds ratio representing clinical improvement. The odds ratio represents the odds of improvement in the ordinal scale for treatment relative to placebo.³ The sample size to detect a given odds ratio for 1:1 randomization using a 2-tailed test at level α is given by

$$\frac{12(z_{\alpha/2} + z_{\beta})^2}{\lambda^2(1 - \sum_{i=1}^K p_i^3)}$$

where λ is the log odds ratio, p_i is the overall probability (combined over both arms) of being in the i th category of the K ordinal outcomes, and $z_{\alpha/2}$ and z_{β} are the $1 - \alpha/2$ and $1 - \beta$ quantiles of the standard normal distribution.

However, to fully understand all aspects of the testing procedure, we have simulated the probabilities of an intervention: a) being declared futile after 50 patients per arm, b) being declared efficacious after 50 patients per arm, and c) being declared promising by 100 patients per arm.

The interim analysis will find an intervention futile if its point estimate for the primary endpoint has an odds ratio < 1. An intervention can be declared efficacious early after 50 patients per arm if two-sided $p < 0.001$. If the intervention continues to 100 patients, it will be declared promising if the final p-value is < 0.20, and statistically significant if the final p-value is < 0.05. More details are provided in Interim Analysis Section.

Table 5 displays the outcome probabilities in the control arm for sample size determination; this uses preliminary unpublished data from the remdesivir arm in ACTT study. The categories of the 8-point ordinal scale are:

1. Not hospitalized, no limitations on activities;
2. Not hospitalized, limitation on activities and/or requiring home oxygen*;
3. Hospitalized, not requiring supplemental oxygen* - no longer requires ongoing medical care;
4. Hospitalized, not requiring supplemental oxygen* - requiring ongoing medical care (COVID-19 related or otherwise);
5. Hospitalized, requiring supplemental oxygen*;
6. Hospitalized, on non-invasive ventilation or high flow oxygen devices;
7. Hospitalized, on invasive mechanical ventilation or ECMO;
8. Death.

*For subjects on chronic supplemental oxygen, this pertains to an increased oxygen requirement above baseline.

Table 5. Expected distribution of ordinal outcomes for the control arm at Day 8

Severity Outcome	Outcome (%)
Not hospitalized, no limitations on activities	0.0
Not hospitalized, limitation on activities and/or requiring home oxygen	34.6
Hospitalized, not requiring supplemental oxygen - no longer requires ongoing medical care	1.2
Hospitalized, not requiring supplemental oxygen - requiring ongoing medical care (COVID-19 related or otherwise)	10.6
Hospitalized, requiring supplemental oxygen	17.1
Hospitalized, on non-invasive ventilation or high flow oxygen devices	8.8
Hospitalized, on mechanical ventilation or ECMO	24.2
Death	3.5

Table 6 provides the probability to detect futility or efficacy given various odds ratios at interim and final analysis based on simulations (with 10,000 replications). An intervention with no effect (an odds ratio of 1) had 50% chance of stopping at the interim analysis and has only a 10% chance to show promise. An intervention with an odds ratio of 2 has high power to show promise; that is, there is 91% probability that the final p-value will be less than .20 and only a 3% chance it will be stopped at an interim futility test. The powers in Table 6 are slightly lower than what would be determined from the Whitehead formula, because there is some minimal trade-off associated with testing for futility, especially for the alpha=.20 significance threshold.

Table 6. Simulated early stopping probabilities at the interim review (n=50/arm), and power calculations for the final study size (n=100/arm) for Day 8 Ordinal Score

OR	Probability of stopping for futility or efficacy at interim analysis for a given true odds ratio		Power at full study enrollment (100 active, 100 control)	
	Futility	Efficacy	Efficacy w/ alpha=.05	Efficacy w/ alpha=.20
0.75	0.793	0.000	0.001	0.008
1.00	0.502	0.000	0.026	0.096
1.25	0.260	0.004	0.136	0.329
1.50	0.126	0.014	0.348	0.604
1.75	0.060	0.036	0.581	0.802
2.00	0.028	0.070	0.765	0.913
2.25	0.013	0.119	0.879	0.961
2.50	0.006	0.179	0.939	0.984

9.2 Populations for Analyses

The primary analysis will be based on a modified intention-to-treat population, including all subjects who received at least one dose of study product. Similarly, safety analyses will be based on a modified intention-to-treat population consisting of all subjects who received at least one study product administration.

9.3 Statistical Analyses

9.3.1 General Approach

This is a proof of concept double-blind placebo controlled randomized trial testing a superiority hypothesis where interventions with a two-sided p-value < .20 will be declared promising, and will be considered statistically significant if the final two-sided p-value is < .05. Both 95% and 80% confidence intervals will be computed for the treatment effect corresponding to the primary and key secondary endpoints. One key secondary hypothesis will be highlighted for each individual intervention in the corresponding appendix. All endpoints will also be described according to the appropriate summary statistics (e.g., proportions for categorical data, means with 95% confidence intervals for continuous data, median for time-to-event data).

A statistical analysis plan will be developed and filed with the study sponsor prior to unblinding of study and database lock.

Unblinding of the study will occur after all subjects enrolled have reached the end of study, the study visits are monitored, and data is cleaned.

9.3.2 Analysis of the Primary Efficacy Endpoint

The ordinal scale will be used to estimate a proportional odds model, with covariate adjustment for baseline steroid use and baseline severity (baseline Ordinal Score 4 and 5 combined versus Ordinal Score 6 and 7 combined). Because of the potential for COVID-19 treatments to emerge, a key supplemental analysis would mimic this primary analysis, but add adjustments for baseline use of each other innovative treatment. The hypothesis test will evaluate whether the common odds ratio for treatment is equal to one. The distribution of baseline steroid (and emerging treatments included in the supplemental analysis) and severity results will be summarized by treatment arm as percentages. Subjects in the shared control arm can only be used in comparison of any given intervention ‘A’, if they were eligible for ‘A’ and consented to randomization to ‘A’; thus controls randomized at clinics where ‘A’ is not currently being studied are not compared to subjects in the ‘A’ arm. Efforts to minimize loss-to-follow-up will be considerable. However, small amounts of missing data may occur. In such cases, subjects without final outcome data will be excluded from the analysis. Sensitivity analyses will evaluate the impact of making different assumptions about missing observations. These analyses will be defined in the SAP.

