
3. To evaluate post-baseline usage of key concomitant COVID-19 treatments (e.g., steroids) in investigational therapeutic arms as compared to the control arm.
	
 ● Type, dose, study day onset, and duration.

4. To evaluate standard of care steroid usage for indications other than COVID-19 post-baseline.
	
 ● Indication (ICD-10 code). ● Steroid type, dose, study day onset, and duration.

**Additional objectives and endpoints are listed in each stage-specific Appendix.*

†Each stage-specific Appendix may designate a different “Key Secondary” and additional “Other Secondary” objective(s)/endpoint(s) if appropriate for the specific intervention being evaluated.

Study Population

This trial will study putative therapeutics in a hospitalized adult population (≥ 18 years old) with COVID-19. The platform trial will have common inclusion criteria but may be modified for each stage for the unique risk of the study product in that stage. Exclusion criteria are described in each stage-specific appendix.

Inclusion Criteria:

1. Admitted to a hospital with symptoms suggestive of COVID-19 and requires ongoing medical care.
2. Subject (or legally authorized representative) provides informed consent prior to initiation of any study procedures.
3. Subject (or legally authorized representative) understands and agrees to comply with planned study procedures.
4. Male or non-pregnant female adult ≥ 18 years of age at time of enrollment.
5. Has laboratory-confirmed SARS-CoV-2 infection as determined by PCR or other commercial or public health assay in any specimen, as documented by either of the following:
 - PCR positive in sample collected < 72 hours prior to randomization; OR
 - PCR positive in sample collected ≥ 72 hours but < 7 days prior to randomization AND nonimproving or progressive disease suggestive of ongoing SARS-CoV-2 infection.

Note: if written documentation of the positive test result is not available at the time of enrollment (e.g., report came from other institution), the subject may be enrolled but the PCR should be repeated at the time of enrollment.

6. Illness of any duration, and at least one of the following:
 - Radiographic infiltrates by imaging (chest x-ray, computed tomography [CT] scan, etc.), OR
 - Blood oxygen saturation (SpO₂) ≤ 94% on room air, OR
 - Requiring supplemental oxygen, OR
 - Requiring mechanical ventilation or ECMO.

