4.3 Randomization

Randomization will be stratified by study site and severity (baseline Ordinal Score 4 and 5 combined versus Ordinal Score 6 and 7 combined).

While the trial is enrolling patients into multiple active interventions, randomization will be a 2-stage process. In stage 1, a patient who is eligible for 3 interventions A, B, C, will be randomized equally (33% chance) to A, B, and C. At stage 2, the patient will be randomized to active or placebo version of the intervention selected in stage 1 with a 75% or 25% chance, respectively. More generally, patients will first be randomized to 1 of the interventions to which they are eligible with equal allocation. Then patients are randomized to the active or placebo version of that intervention with allocation $k:1$, where k is the number of interventions for which a subject is eligible. For example, if a patient is eligible for 3 active treatments that the site is currently randomizing, the patient will be randomized to 1 intervention with a 1:1:1 allocation to the 3 interventions, then randomized to 1 treatment with a 3:1 allocation of active versus placebo. This process results in equal allocation of the 3 intervention arms and the pooled placebo arm.

Differing entry criteria across interventions adds complexity to this process. Patients who are eligible for all 3 interventions will be randomized to A, B, or C in the first stage, and then have a 25% chance of randomization to placebo in the second stage. However, the patient who is not eligible for C will first be randomized to A and B with equal probability, and will have a 33% chance of randomization to placebo in the second stage, leading to equal size A, B, and pooled placebo groups for this stratum of patients. Ultimately, evaluation of A versus placebo would need to only include subjects that were eligible to be randomized to A. The statistical analysis plan (SAP) will provide details.

The previous paragraph refers to a scenario in which the interventions have largely overlapping study populations. However, at some point the trial might study agents for non-overlapping cohorts. For example, there might be one or multiple interventions that are only appropriate for subjects who have a baseline Ordinal Score of 4 or 5, and a completely different set of

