 - Creatinine (and calculate eGFR).

- Any automated calculation by the clinical laboratory or published formula for this calculation is acceptable. The site should select a formula to be used for all subjects enrolled at the site for the duration of the study.
- Urine or serum pregnancy test (in women of childbearing potential).

Clinical screening laboratory evaluations will be performed locally by the site laboratory.

The overall eligibility of the subject to participate in the study will be assessed once all screening values are available. Complete the inclusion and exclusion criteria checklists on the day of enrollment as these forms include data needed to register all potential subjects in the electronic data capture (EDC) system. The screening process can be suspended prior to complete assessment at any time if exclusions are identified by the study team.

Study subjects who qualify will be randomized in the interactive response technology system (IRT) system, and all others will be registered as screen failures only in the EDC system. The study team has 24 hours to complete Day 1 baseline assessments prior to the first study product administration including the collection of OP swab and blood, assessment of the ordinal scale and NEWS and completing or recording a baseline physical examination that was done.

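### The primary Day 8 model adjusts for baseline severity in two levels although the four-level score is collected: a valid analysis that gives up some efficiency

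*Protocol*

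**What the plan says.** Section 9.3.2 specifies a proportional odds model for the Day 8 ordinal score; it is to be fitted "with covariate adjustment for baseline steroid use and baseline severity (baseline Ordinal Score 4 and 5 combined versus Ordinal Score 6 and 7 combined". The key supplemental analysis in the same section adds only baseline use of other emerging treatments. No analysis in the protocol adjusts for the score at its full resolution.

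The two-level split is the one used at allocation. Section 4.3 states: "Randomization will be stratified by study site and severity (baseline Ordinal Score 4 and 5 combined versus Ordinal Score 6 and 7 combined". Section 9.3.8 uses it again for the severity subgroup.

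The full score is available. Section 8.1.1 lists "assessment of the ordinal scale and NEWS" among the Day 1 assessments to be completed before the first study product administration. Inclusion criterion 1 in Section 1.1 ("Admitted to a hospital with symptoms suggestive of COVID-19 and requires ongoing medical care"), together with the strata, means that the possible baseline levels are 4, 5, 6 and 7.

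Section 9.3.3 (item 4) analyses the later ordinal scores in the same way as Day 8, so the same covariate carries over to them.

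**The concern.** The outcome is the baseline scale measured a week later, so the baseline score can be expected to be a strong predictor of it. The planned covariate gives a subject on invasive ventilation or ECMO (7) the same expected Day 8 distribution as one on non-invasive ventilation or high-flow oxygen (6). It does the same for a subject on no oxygen (4) and one on supplemental oxygen (5). Randomization is stratified by site and by the same two-level split, so chance imbalance between 6 and 7, or between 4 and 5, is neither prevented by design nor adjusted for in the model.

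Two things are at stake. One is power at the p<.20 threshold that decides whether an agent is called promising. The other is the odds ratio passed on to later trials, since Section 9 says that the estimates will inform their design. The interim futility guideline is a bare point estimate below 1 at about 50 per arm, so a single trial with a visible imbalance within one half is also exposed.

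**Working it through.** **1. Reproducing the plan's own figures.** Section 9.1 states "We have chosen a sample size of 100 per arm for this proof of concept study" and gives the Whitehead formula "for 1:1 randomization using a 2-tailed test". The inputs are N = 200, λ = ln 2 = 0.693 and the Table 5 control distribution. Applying an odds ratio of 2 and averaging the two arms gives Σp³ = 0.0922. Then

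Z = √[N λ² (1 − Σp³)/12] = √[200 × 0.4805 × 0.9078/12] = 2.696.

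Power is Φ(2.696 − 1.960) = 0.769 at α = .05 and Φ(2.696 − 1.282) = 0.921 at α = .20. Table 6 gives 0.765 and 0.913, slightly lower because of the interim look, as Section 9.1 says. A simulation of the two-look rule (100,000 replicates, unadjusted score test) at an odds ratio of 2 gives futility 0.029, interim efficacy 0.072, and power 0.762 and 0.909. Table 6 has 0.028, 0.070, 0.765 and 0.913. Table 6 therefore reproduces as a calculation without covariates.

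**2. Two levels against four.** The protocol gives neither the baseline mix nor the prognostic gradient, so both are assumed. The true odds ratio conditional on the four levels is set to 2. Intercepts are calibrated so that the control margin equals Table 5. Steroid use is left out because no rate is given. Large-sample fits at 100 per arm, without the interim, use power = Φ(Z − z) with z = 1.282 (α = .20) or 1.960 (α = .05). The effective-sample-size ratio is (Z four-level / Z two-level)². The four-level model returns 2.00 throughout.

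| Mix 4/5/6/7 (%) | Log-odds at 4, 5, 6, 7 | OR, two-level | Z two → four | Ratio | Power at .20 | Power at .05 |
|---|---|---|---|---|---|---|
| 25 each | 0, 0.5, 1, 1.5 | 1.98 | 2.596 → 2.622 | 1.02 | .906 → .910 | .738 → .746 |
| 25 each | 0, 1, 2, 3 | 1.93 | 2.448 → 2.542 | 1.08 | .878 → .896 | .687 → .720 |
| 25 each | 0, 1.5, 3, 4.5 | 1.87 | 2.267 → 2.449 | 1.17 | .838 → .879 | .621 → .688 |
| 10/40/30/20 | 0, 0.5, 1, 1.5 | 1.985 | 2.612 → 2.633 | 1.02 | .908 → .912 | .743 → .750 |
| 10/40/30/20 | 0, 1, 2, 3 | 1.95 | 2.502 → 2.577 | 1.06 | .889 → .902 | .706 → .731 |
| 10/40/30/20 | 0, 1.5, 3, 4.5 | 1.90 | 2.365 → 2.507 | 1.12 | .861 → .890 | .658 → .708 |
| 10/40/30/20 | 0, 0.3, 2, 2.3 | 1.995 | 2.561 → 2.568 | 1.01 | .900 → .901 | .726 → .728 |

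The last row is the case in which levels within a pair have similar prognosis: almost nothing is gained.

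Over 20 such scenarios (four mixes, five gradients) the two-level odds ratio ran from 1.86 to 1.995. The gain from four levels was 0.1 to 4.1 points at α = .20 and 0.2 to 7.1 points at α = .05. The unadjusted odds ratio was 1.57 to 1.95, so the planned covariate usually recovers most of what adjustment can offer.

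**3. Finite-sample check.** Simulation at 100 per arm (600 to 1,000 replicates per cell, 0.5 to 1.5 log-odds per level) gave 1-14% more effective sample size. Power changed by about 0 to 5 points at p<.20 and 0.5 to 6 points at p<.05. Null error stayed close to nominal under the four-level model, including at 50 per arm. The 17% in the table is the extreme corner of the large-sample fits.

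**4. Interim futility.** This used 2,500 simulated interims per scenario at 50 per arm and 1.0 log-odds per level, with mixes 13/41/18/28, 15/50/20/15 and 25% each. Averaged over all trials at a true odds ratio of 2, the futility stop rate was 3.6-4.8% with two levels and 3.7-4.0% with four. In the 12-17% of trials where the active arm had at least four more baseline-7 subjects than control, the rates were 5.3-7.5% and 3.4-3.8%.

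**The case against.** Adjusting for the stratification factor is conventional, and nothing in the protocol is contradictory here. The two-level model estimates a legitimate parameter, the odds ratio conditional on the stratum, and chance imbalance within a stratum is already reflected in its standard error. All of this stands.

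The magnitudes also depend on what an odds ratio of 2 means. Table 6 is unadjusted, so its 2 can be read as a marginal value. In simulations with the marginal odds ratio set to 2 (mixes 13/41/18/28 and 15/50/20/15, 0.8 and 1.6 log-odds per level, 1,000 replicates, no interim), the two-level model already has power 0.947-0.990 at p<.20. Four levels changes that by −0.3 to +1.4 points. This stands too: the larger gains belong to the conditional reading. The top of the assumed range is also steep: 1.5 log-odds per level means odds differing e^1.5 ≈ 4.5-fold between adjacent levels and e^4.5 ≈ 90-fold from level 4 to level 7.

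A reader might infer three stronger things. The first is that the planned odds ratio is biased. It is not: the shift toward 1 is non-collapsibility, and the value under the null remains 1. The second is that Table 6 overstates power. The protocol presents it as a calculation without covariates, and it reproduces. The third is that the futility guideline will often discard good agents because of this coding. On average the change is about a point or less (0 to 1.7 points in one further set of runs with a conditional odds ratio of 2), and Section 9.3.7 makes the rule a guideline that the DSMB may use.

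What remains is that, under the conditional reading, the four-level model was at least as efficient in every scenario tried, for almost no cost.

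**Conclusion.** The point holds as an efficiency weakness, not as an error. On the assumptions above, the coding gives up about 1-14% of effective sample size and up to about 5 points of power at the decision threshold. At 1.0 log-odds per level the loss at p<.20 is 1.3 to 1.8 points and the two-level odds ratio is 1.93-1.95 instead of 2.00. The direction is firm whenever 4 differs from 5, or 6 from 7, in prognosis. The size is not firm, because the baseline mix and gradient are assumed and steroid use was not modelled. At the interim the benefit is mainly protection in a particular trial with chance imbalance inside a severity half, not a lower average stopping rate.

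**What to change.** In Section 9.3.2, replace the two-level severity covariate with baseline ordinal score as a four-level factor (4, 5, 6, 7), keeping baseline steroid use. Apply the same model at the interim and in the analogous later ordinal-score analyses of Section 9.3.3. State in advance that adjacent levels are merged, within a severity half only, if one is too sparse to estimate. Keep the two-level split for randomization and for the subgroup analysis. Leave Table 6 as it is.

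The four-level factor contains the two-level split, so the severity stratum is still respected. The cost is two extra parameters and a change of wording before unblinding, with no new data. If the sponsor prefers to keep the planned model as primary, the least that should be done is to pre-specify the four-level model as a sensitivity analysis.
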